4.5.4 Life Style Guidelines

Patients who are biologically capable of having children and sexually active must agree to use at least 2 acceptable methods of birth control, one of which must be highly effective for the duration of the treatment period and for at least 6 months after the last dose of study

treatment. The Investigator will counsel the patient on selection of contraception method and instruct the patient in its consistent and correct use.

Examples of acceptable birth control methods considered highly effective are the following:

1. Oral, inserted, injected or implanted hormonal methods of contraception, provided it has been used for an adequate period of time to ensure effectiveness.
2. Correctly placed copper containing intrauterine device (IUD).
3. Male sterilization with confirmed absence of sperm in the post-vasectomy ejaculate.
4. Bilateral tubal ligation or bilateral salpingectomy.
5. Sexual abstinence (in the context of this protocol, sexual abstinence is considered a highly effective method of birth control only if refraining completely from heterosexual intercourse during the entire period of risk (i.e., during study treatment, including during temporary breaks from treatment, and for at least 6 months after stopping study treatment)).

Acceptable birth control methods not considered highly effective include the following:

1. Progestogen-only oral hormonal contraception, where inhibition of ovulation is not the primary mode of action
2. Male or female condom with spermicide
3. Cap, diaphragm, or sponge with spermicide

The Investigator will instruct the patient to call immediately if the selected birth control method is discontinued or if pregnancy is known or suspected.

Note: Women are considered post-menopausal and/or not of child bearing potential if they have had 12 months of natural (spontaneous) amenorrhea with an appropriate clinical profile (e.g., age appropriate, history of vasomotor symptoms) or have had surgical bilateral oophorectomy (with or without hysterectomy) or tubal ligation at least 6 months ago. In case of any ambiguity, the reproductive status of the woman should be confirmed by hormone level assessment.

4.6 Method of Assignment/Randomization

Following review of all screening procedures, patient eligibility will be confirmed by appropriately qualified staff at the investigational site. Patients will be enrolled to 1 of the 2 cohorts based on PD-L1 status, TPS \geq 50% and TPS 1-49%. Within each cohort, patients will initially be randomized 1:1 to either the Group A (“main study population”) or Group B (“pembrolizumab run-in population”). Randomization in each cohort will continue until 5 patients have been enrolled to Group 1B and 5 patients have been enrolled to Group 2B. The randomized portion of the study will be performed exclusively at Yale. All subsequent patients will be assigned (not randomized) to Group A. This study will not be blinded.

5 Study Treatments

The investigational treatments to be used in this trial are the novel drug sitravatinib and FDA approved therapy pembrolizumab.

5.1 Sitravatinib

Sitravatinib is a spectrum-selective RTK inhibitor that acts on several closely related RTKs including the TAM family (Tyro3/Axl/MERTK), VEGFR2, KIT, and MET. This drug is currently experimental and is not FDA approved. It is administered as a daily oral medication.

5.1.1 Sitravatinib Formulation, Packing and Storage

The sitravatinib formulation used in this protocol is the malate salt capsule product which consists of a blend of sitravatinib malate salt drug substance, microcrystalline cellulose, mannitol, colloidal silicon dioxide, croscarmellose sodium, colloidal silicon dioxide and magnesium stearate. The blend is filled into hard gelatin capsules.

Sitravatinib drug product is packaged in high-density polyethylene (HDPE), white opaque, round 60 cc bottles. A tamper-proof heat induction seal and a child-resistant closure are used. The provided bottles may be labeled for specific patient use and given to the patient. Sitravatinib medication labels comply with the legal requirements of the US.

Investigational clinical trial material must be stored in an area that is secure, with limited access and monitored for temperature using a calibrated thermostat or thermometer. Only

qualified personnel who are familiar with procedures that minimize undue exposure to them and to the environment should undertake the preparation, handling, and safe disposal of small molecule therapeutic agents. Sitravatinib capsules should be stored under the conditions stated on the container labels and the Pharmacy Study Manual.

Please Refer to the Pharmacy Study Manual for further details.

5.1.2 Sitravatinib Schedule and Administration

Sitravatinib capsules will be administered orally, once per day (QD), as a continuous regimen expressed in 21-day cycles. The starting dose of the sitravatinib malate capsule formulation is 100 mg QD. For patients in Groups 1A and 2A (main study population), sitravatinib dosing will begin on C1D1. For patients in Groups 1B and 2B (pembrolizumab run-in population) dosing of sitravatinib will begin on C2D1 of the study.

The following guidelines should be followed for sitravatinib administration:

- Dosing in the morning is preferred.
- Capsules should be taken on an empty stomach (at least 2-hour fast before each dose and no food for a minimum of 1 hour after each dose) until notified otherwise by the Sponsor.
- Capsules should be taken with at least 240 mL (approximately 1 cup) of water.
- Patients should swallow the capsules whole and not chew them.
- If vomiting occurs after dosing, sitravatinib doses should not be replaced.
- Missed doses should be taken within 12 hours of the scheduled time and the next dose should be taken at its scheduled time.

Additional details are provided in the Pharmacy Study Manual.

5.1.3 Sitravatinib Dose Modification or Discontinuation

Depending on safety observations, the sitravatinib dose during subsequent cycles of treatment may be reduced as per *Table 1*. Indications for dose modification and treatment delay are discussed in Section 5.3.1 (Management of Sitravatinib Adverse Events). Once the dose has been reduced, re-escalation is generally not recommended but may be considered on a case-by-case basis after discussion with the Sponsor Investigator. If the administration of sitravatinib is interrupted for reasons other than toxicity then treatment with the study drug may be resumed at the same dose.

Although sitravatinib has not been associated with irAEs, it may potentiate the effect of pembrolizumab and contribute to irAEs. Therefore, for any AE that requires interruption of pembrolizumab, sitravatinib should also be interrupted until the event improves to Grade ≤1. Please see section 5.3.1 for management of sitravatinib in the case of irAEs.

In the case of an AE that can clearly be attributed to sitravatinib and is not immune-mediated (ie hypertension), dose reduction with continuous treatment is preferred over repeated dose interruption. If treatment with sitravatinib is delayed for ≥ 14 days due to AEs, then resumption will be at a reduced dose. If treatment with sitravatinib is withheld for ≥ 28 consecutive days due to AEs, then sitravatinib will be permanently discontinued unless reviewed and approved by the Sponsor Investigator. In the case of interruption or discontinuation of sitravatinib, pembrolizumab may be continued at the discretion of the Treating Investigator if the AE is attributed to sitravatinib alone. If pembrolizumab is discontinued due to toxicity, the continuation of sitravatinib as monotherapy may be considered once the AE improves to Grade ≤1 and following discussion with the Sponsor- Investigator.

Table 1: Sitravatinib Sequential Dose Reductions for Individual Patients on Malate Capsule Formulation

100 mg once daily
70 mg once daily
50 mg once daily
35 mg once daily

5.1.4 Sitravatinib Dispensing and Accountability

Dispensing of sitravatinib will be performed as per the Pharmacy Study Manual. Receipt and dispensing of study drug must be recorded by an authorized person at the study site. Study drug may not be used for any purpose other than that stated in the Protocol.

Patients will be asked to record their daily dosing in a pill dairy (Appendix 6), and report any missed doses or lost doses at the next clinic visit. Patients should be told to bring study

treatment bottle(s) (empty or not) and completed dosing diaries with them to the clinic visit for a compliance check and capsule count.

At the end of the study, all unused sitravatinib drug supplies must be destroyed in accordance with local Standard Operating Procedure, or returned to the manufacturer.

5.2 Pembrolizumab

Pembrolizumab is a potent and highly selective humanized monoclonal antibody (mAb) of the IgG4/kappa isotype designed to directly block the interaction between PD-1 and its ligands, PD-L1 and PD-L2. Keytruda™ (pembrolizumab) is approved in the United States as monotherapy for the treatment of patients with unresectable or metastatic NSCLC and PD-L1 expression $\geq 1\%$.

5.2.1 Pembrolizumab Formulation, Packing and Storage

Pembrolizumab will be provided commercially for patients as an FDA approved therapy for treatment naïve patients with PD-L1 positive NSCLC.

Refer to the current pembrolizumab approved product insert for further details on formulation, packing and storage information.

5.2.2 Pembrolizumab Schedule and Administration

All patients will receive pembrolizumab 200mg administered as a 30 minute IV infusion every 3 weeks starting on study Day 1. Treatment will be continued for 35 cycles or until progression, unacceptable toxicity, withdrawal of consent or study end, whichever occurs first. Patients with progression of disease by RECIST v1.1 may be allowed to continue trial therapy as per Section 6.8 at the discretion of Sponsor Investigator.

Further administration details as per current pembrolizumab product label.

5.2.3 Pembrolizumab Dose Modification or Discontinuation

Interruption or discontinuation of pembrolizumab may be required for some toxicities as summarized in *Table 2*. Treatment of suspected pembrolizumab related adverse events is discussed in Section 5.3.3. Dose reductions of pembrolizumab are not allowed. Dosing interruptions are permitted in the case of medical / surgical events or logistical reasons not

related to study therapy (e.g., elective surgery, unrelated medical events, patient vacation, and/or holidays). Subjects should be placed back on study therapy within 3 weeks of the scheduled interruption, unless otherwise discussed with the Sponsor Investigator. The reason for interruption should be documented in the patient's study record.

Table 2: Dose Modification Guidelines for Drug-Related Adverse Events for Pembrolizumab

Toxicity	Hold Treatment For Grade	Timing for Restarting Treatment	Discontinue Subject
Diarrhea/Colitis	2-3	Toxicity resolves to Grade 0-1.	Toxicity does not resolve within 12 weeks of last dose or inability to reduce corticosteroid to 10 mg or less of prednisone or equivalent per day within 12 weeks.
	4	Permanently discontinue	Permanently discontinue
AST, ALT, or Increased Bilirubin	2	Toxicity resolves to Grade 0-1	Toxicity does not resolve within 12 weeks of last dose.
	3-4	Permanently discontinue (see exception below) ¹	Permanently discontinue
Type 1 diabetes mellitus (if new onset) or Hyperglycemia	T1DM or 3-4	Hold pembrolizumab for new onset Type 1 diabetes mellitus or Grade 3-4 hyperglycemia associated with evidence of beta cell failure.	Resume pembrolizumab when patients are clinically and metabolically stable.
Hypophysitis	2	Toxicity resolves to Grade 0-1	Toxicity does not resolve within 12 weeks of last dose or inability to reduce corticosteroid to 10 mg or less of prednisone or equivalent per day within 12 weeks.
	3-4	Withhold until clinically stable or permanently discontinue depending on severity	Permanently discontinue depending on severity.
Hyperthyroidism	3-4	Withhold until clinically stable or permanently discontinue depending on severity	Toxicity does not resolve within 12 weeks of last dose or inability to reduce corticosteroid to 10 mg or less of prednisone or equivalent per day within 12 weeks.
Hypothyroidism	2-4	Therapy with pembrolizumab can be continued while treatment for the thyroid disorder is instituted	Therapy with pembrolizumab can be continued while treatment for the thyroid disorder is instituted.
Infusion Reaction	3-4	Permanently discontinue	Permanently discontinue
Pneumonitis	2	Toxicity resolves to Grade 0-1	Toxicity does not resolve within 12 weeks of last dose or inability to reduce corticosteroid to 10 mg or less of prednisone or equivalent per day within 12 weeks.
	3-4	Permanently discontinue	Permanently discontinue
Renal Failure or Nephritis	2	Toxicity resolves to Grade 0-1	Toxicity does not resolve within 12 weeks of last dose or inability to reduce corticosteroid to 10 mg or less of prednisone or equivalent per day within 12 weeks.
	3-4	Permanently discontinue	Permanently discontinue

Toxicity	Hold Treatment For Grade	Timing for Restarting Treatment	Discontinue Subject
All Other Drug-Related Toxicity ²	3 or Severe	Toxicity resolves to Grade 0-1	Toxicity does not resolve within 12 weeks of last dose or inability to reduce corticosteroid to 10 mg or less of prednisone or equivalent per day within 12 weeks.
	4	Permanently discontinue	Permanently discontinue
Note: Permanently discontinue for any severe or Grade 3 drug-related AE that recurs or any life-threatening event.			
¹ For patients with liver metastasis who begin treatment with Grade 2 AST or ALT, if AST or ALT increases by greater than or equal to 50% relative to baseline and lasts for at least 1 week then patients should be discontinued. ² Patients with intolerable or persistent Grade 2 drug-related AE may hold study medication at physician discretion. Permanently discontinue study drug for persistent Grade 2 adverse reactions for which treatment with study drug has been held, that do not recover to Grade 0-1 within 12 weeks of the last dose.			

5.3 Management of Adverse Events

A complete review of adverse events should be conducted at each clinic visit with laboratory assessment as per Study Calendars (Section 6.1).

5.3.1 Sitravatinib-Related Adverse Events

5.3.1.1 General Management of Sitravatinib Related Non-Hematologic Toxicities

General management of non-hematologic sitravatinib related toxicities are summarized in *Table 3*. Symptomatic Grade 2 sitravatinib-related non-hematological adverse events occurring any time on study, particularly early in treatment, are managed using dose reduction to the next lower dose level, per the reduction schedule outlined in *Table 1*, rather than continued dosing until interruption becomes necessary.

Non-hematological toxicities \geq Grade 3 and considered to be related to sitravatinib treatment will be managed with sitravatinib interruption, with or without dose reduction, until resolution of toxicity to \leq Grade 1 or to baseline value. If the toxicity is adequately managed by routine supportive care (such as electrolyte supplementation), treatment may be resumed at the same dose; otherwise, treatment may be resumed at one or more levels below the dose level where toxicity was observed as outlined in *Table 1*. Recurrence of a toxicity may be managed similarly. If treatment is interrupted for \geq 28 days, sitravatinib will be permanently discontinued unless reviewed and approved by the Sponsor Investigator.

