5.3.1.2 General Management of Sitravatinib Related Hematological Toxicities

Hematological toxicities are not a frequent cause of treatment interruption or discontinuation of sitravatinib treatment. Observed \geq Grade 3 hematological events that are considered to be causally related to sitravatinib should initially be managed using treatment interruption until resolution of toxicity to \leq Grade 2. In addition, dose reduction of sitravatinib will be implemented in the following cases:

- Grade 3 or 4 febrile neutropenia;
- Grade 4 neutropenia persisting for \geq 8 days; or
- Grade 4 thrombocytopenia of any duration or Grade 3 thrombocytopenia with bleeding.

Table 3: Dose Modifications for Sitravatinib Toxicity

Toxicity	Grade	Treatment Delay	Dose Modification
General non-hematologic toxicity ¹	1	Not required	None
	2	Not required	Asymptomatic: None required
			Symptomatic: None required. Early dose reduction to the next lower dose level is recommended over treatment interruption.
	3-4	Hold until \leq grade 1 or return to baseline	Resume at reduced dose. Exceptions presented in footnotes ²
Hematologic toxicities	1-2	Not required	None
	3	Hold until \leq grade 2	Reduce dose for grade 3 febrile neutropenia or grade 3 thrombocytopenia with bleeding
	4	Hold until \leq grade 2	Reduce for grade 4 febrile neutropenia, grade 4 neutropenia lasting \geq 8 days or grade 4 thrombocytopenia
Hypertension	1-2	Not required	None required
	3	Not clinically significant ³ : Not required	Decrease dose if unresponsive to anti-hypertensive treatment
		Clinically significant ³ : Hold until \leq grade 2 or return to baseline	Resume at decreased dose level
	4	Discontinue	Discontinue
Transaminitis	1	Not required	None required
	2	Not required	Decrease by one dose level
	3-4	Hold until \leq grade 1 or return to baseline	If resolution occurs within 29 days, decrease by 1 dose level. If no resolution within 29 days, discontinue sitravatinib

¹ Management of selected sitravatinib toxicities as per Section 5.3.2

² Patients may resume at the same dose in the following cases:

- a. Grade 3 or 4 electrolyte abnormality that is not clinically complicated and resolves spontaneously or with conventional medical treatment within 72 hours;

b. Grade 3 amylase or lipase elevation that is not associated with symptoms or other clinical (e.g., electrolyte abnormalities, radiographic changes) manifestations of pancreatitis.

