Increased amylase and lipase have been observed in subjects treated with sitravatinib and have been reported with other inhibitors of the VEGF pathway. Most sitravatinib-related treatment-emergent events of increased amylase and lipase were asymptomatic while some were associated with signs and/or symptoms of pancreatitis. Treatment with sitravatinib may continue without dose modification (eg, interruption or reduction) in cases of asymptomatic

amylase and/or lipase increases in the absence of other clinical evidence of pancreatitis (eg, symptoms, electrolyte abnormalities, radiographic changes) at the Treating Investigator's discretion. Sitravatinib should be interrupted for any grade pancreatitis and the subject managed according to standard-of-care. After resolution of pancreatitis, sitravatinib resumption is at the discretion of the Treating Investigator; if pancreatitis is assessed as sitravatinib treatment-related and treatment is resumed, a dose reduction is recommended.

Immune-Related Adverse Events (irAEs)

Single agent sitravatinib has not been associated with irAEs. However, the potential exists for irAEs associated with sitravatinib to contribute to irAEs associated with pembrolizumab treatment. In the event of a Grade 2 irAE during study treatment, administration of sitravatinib and pembrolizumab will be interrupted until the event stabilizes to Grade ≤ 1 (see Section 5.3.3 on pembrolizumab associated adverse event treatment). At the time of resumption of sitravatinib dosing, a dose reduction may be implemented at the discretion of the Treating Investigator.

Management of Grade 3 and 4 irAEs should be performed as in section on pembrolizumab related adverse events management (Section 5.3.3). Recurrent Grade 3, or any Grade 4, irAEs should generally be managed with permanent discontinuation of pembrolizumab, and temporary or permanent interruption of sitravatinib. Sitravatinib may be resumed at the same or lower dose at the discretion of the Treating Investigator once the event stabilizes to Grade ≤ 1 .

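### Sections 5.3.1.1 and 5.1.3 and Table 3 lead to different sitravatinib doses after the same toxicity hold, and no passage says which one governs

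*Combined protocol and SAP*

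**What the plan says.** Four places in the protocol set out what happens to sitravatinib after a toxicity.

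- **Section 5.3.1.1** (non-hematologic toxicity). Grade 3 or higher events are held until Grade 1 or baseline. Then: "If the toxicity is adequately managed by routine supportive care (such as electrolyte supplementation), treatment may be resumed at the same dose"; otherwise the restart may be one or more levels lower. A hold of 28 days or more is permanent unless the Sponsor Investigator approves. Symptomatic Grade 2 events "are managed using dose reduction to the next lower dose level".
- **Table 3** (printed under Section 5.3.1.2, and named in 5.3.1.1 as its summary). For Grade 3-4 general non-hematologic toxicity: "Resume at reduced dose. Exceptions presented in footnotes". Footnote 2 gives two exceptions: an uncomplicated Grade 3-4 electrolyte disturbance that clears within 72 hours, and a Grade 3 rise in amylase or lipase with no sign of pancreatitis. For Grade 2: "Symptomatic: None required. Early dose reduction to the next lower dose level is recommended over treatment interruption". For Grade 3-4 transaminitis, resolution within 29 days leads to a one-level reduction; beyond that, "If no resolution within 29 days, discontinue sitravatinib".
- **Section 5.1.3.** After an AE delay of 14 days or more, "then resumption will be at a reduced dose". After 28 consecutive days or more, "then sitravatinib will be permanently discontinued unless reviewed and approved by the Sponsor Investigator". Both sentences stand in a paragraph that opens with AEs clearly due to sitravatinib and not immune-mediated.
- **Section 5.3.2** (selected events). On transaminases judged not likely to be immune-related, it calls the Table 3 modifications recommended and leaves decisions to the Treating Investigator. After recurrent Grade 3 or any Grade 4 irAE: "Sitravatinib may be resumed at the same or lower dose at the discretion of the Treating Investigator", once the event has settled.

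Table 3 footnote 1 refers selected toxicities to Section 5.3.2. Nothing ranks 5.1.3, 5.3.1.1 and Table 3 against each other.

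**The concern.** A summary table should not be stricter than the text that it summarizes. Here it is: the text opens same-dose resumption to any adequately managed event, and the table closes it to two. Section 5.1.3 then adds a time limit that 5.3.1.1 does not carry. Two investigators who both follow the protocol can give different doses after the same Grade 3 event.

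Sitravatinib is investigational, and Section 4.4.4.1 says that the safety of the combination has not been evaluated in the first-line setting. Adverse events are a secondary endpoint in all groups (Section 4.4.2). If the restart dose depends on which page was read, then exposure, tolerability and discontinuation data depend on it too. So does the count of deviations, because the same act complies with one passage and breaches another. Section 9.2.1 allows sub-analyses that leave out major protocol violations or early discontinuations, so the ambiguity can reach those sets as well.

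**Working it through.** This is a comparison of texts; no sample size, power or error rate enters. Each case below is one event taken through each rule.

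1. **Grade 3 fatigue, controlled by supportive care, 5-day hold.** Section 5.3.1.1: same dose permitted. Table 3: reduced dose, since fatigue is in neither exception. The two conflict.
2. **Grade 3 electrolyte abnormality, corrected by supplementation on day 5.** Section 5.3.1.1: same dose permitted; this is its own example. Table 3: 5 days is 120 hours, beyond the 72-hour exception, so reduced dose. The two conflict.
3. **Grade 3 non-immune event due to sitravatinib, managed by supportive care, 15-day hold.** Section 5.3.1.1: same dose permitted. Section 5.1.3: 15 is at least 14, so reduced dose. The two conflict, and no question about irAEs arises.
4. **Grade 3 transaminitis resolving on day 28 or 29 of a hold.** Sections 5.1.3 and 5.3.1.1: permanent discontinuation unless the Sponsor Investigator approves. Table 3: resume one level lower. This assumes that both clocks start together; Table 3 counts days to resolution, the sections count days of interruption, and Table 3 does not state its starting point.
5. **Grade 3 transaminitis unresolved after day 29.** Sections 5.1.3 and 5.3.1.1: continuation is possible with approval. Table 3: discontinue, with no override.
6. **Symptomatic Grade 2 event, no dose change made.** Section 5.3.1.1 reads as if reduction were the rule. Table 3 does not require it but recommends it early. Both favor reduction; they differ in whether leaving the dose unchanged departs from the protocol.

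Cases 1 to 3 are the core. Cases 4 to 6 are minor.

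**Can the number of affected patients be derived?** Section 1.3.5.1 gives sitravatinib-related Grade 3 events in 485 of 1106 pooled subjects: 485 / 1106 = 0.439, which reproduces the stated 44%. Grade 3 hypertension, which has its own row in Table 3, is 16%. Subjects with a non-hypertension Grade 3 event are therefore at least 44% - 16% = 28%. To reach patients affected by the conflict, one would also need the share with events under the general non-hematologic row, the share that supportive care manages adequately, and the share outside footnote 2 (or, for case 3, held 14 days or more). The documents give none of these for the general row as a whole.

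**The case against.** The best defense is that the passages can be read together. Section 5.3.1.1 says that the same dose may be used, so an investigator who follows Table 3 breaches neither text. Both agree on holding Grade 3 or higher non-hematologic events until Grade 1 or baseline. A specific row such as transaminitis can be taken to override a general rule, and Section 5.3.2 softens that row to a recommendation. Dose intensity is not a listed endpoint, there are at most two sites, and the primary analysis is unchanged.

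Part of this stands. The transaminitis day count differs only on days 28 and 29, although the missing override is a real difference beyond that. The Grade 2 difference is one of wording strength.

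The core survives. A permission in one passage and a requirement in another still mean that a same-dose restart after, say, Grade 3 fatigue complies with 5.3.1.1 and breaches Table 3. That a specific row overrides a general rule is stated nowhere.

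Three stronger readings are tempting and are not supported:

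- *The irAE text in 5.3.2 contradicts the 14-day rule.* The 14-day sentence is in a paragraph that opens with non-immune AEs, and the paragraph before it treats irAEs separately. Two rules for two kinds of event is a natural reading. The 14-day and 28-day sentences themselves speak of AEs without qualification, so their scope is unclear, but a contradiction is not shown.
- *Section 5.3.2 conflicts on when a hold becomes permanent.* It sets no day count for that.
- *About 20 of 70 patients would be affected* (0.28 x 70 = 19.6). That figure counts patients with a non-hypertension Grade 3 event, if pooled rates from other tumors and regimens carried over. It does not count patients who meet the conflict.

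**Conclusion.** The inconsistency is real and lies in the current text. For a Grade 3 or higher non-hematologic event that supportive care manages adequately, Section 5.3.1.1 permits a dose that Table 3 rules out in all but two situations, and that Section 5.1.3 rules out after 14 days for non-immune events. No order of precedence is stated. The transaminitis and Grade 2 mismatches are minor, and the reach of the 14-day and 28-day rules to irAEs is an open question of scope.

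The number of patients affected cannot be given. The 28% is a lower bound for pooled subjects with any non-hypertension Grade 3 event and nothing more. The effect is on consistency of dosing and on exposure, discontinuation, deviation and tolerability data; the primary analysis, sample size and error rates do not change. It should be corrected because the instructions concern the dose of an unapproved drug. Which rule is clinically right is not judged here.

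**What to change.** Reconcile Sections 5.1.3, 5.3.1.1 and 5.3.2 and Table 3 so that each of these has one rule: the dose at resumption after a Grade 3 or higher non-hematologic event; the dose after a delay of 14 days or more; the day count, its starting point and any override for permanent discontinuation, including transaminitis; and whether dose reduction for symptomatic Grade 2 events is required or recommended. State which passage governs if the texts differ, and whether the 14-day and 28-day rules apply to irAEs. Correct the cross-reference in 5.1.3, which sends the reader to Section 5.3.1 for irAEs although that text is in 5.3.2. The sponsor-investigator decides the clinical content.

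The cost is a clarification amendment and a site notice. No procedures, visits or patients are added.
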